8.6. Assessment and Visit Windows

The following time-related windows will be acceptable based on logistical and operational considerations:

- Out Patient Week Visits: as follows, unless otherwise indicated by the investigator:
 - Week 4 \pm 3 days (Visit 3);
 - Week 12 \pm 2 weeks (Visit 4);
 - Week 24 \pm 2 weeks (Visit 5);
 - Week 52 \pm 2 weeks (Visit 6);

- Week 64 \pm 2 weeks (Visit 7a and 7b)

AND if ongoing AEs are being followed;

- Week 76 \pm 2 weeks (Visit 8).
- Week 89 \pm 2 weeks (Visit 9).
- Week 104 \pm 2 weeks (Visit 10).

At all-time points where multiple assessments are performed and blood samples are collected, vital signs measurements (when relevant) will be performed before blood sampling.

Any deviations from the above-mentioned permissible window periods will be documented as protocol non-compliances and will be evaluated for significance at the data review meeting prior to database lock.

8.7. Unscheduled Visits

In the event that a participant reports a potential AE by telephone or other means in between regularly scheduled visits, an unscheduled visit may be performed to do a more detailed analysis of the event. The assessments to be performed at unscheduled visits are at the discretion of the investigator but could include for example, a repeat M.I.N.I. examination if the subject reports a new psychiatric symptom or to repeat any questionable ophthalmic test results that may need to be repeated or validated ([Marmor 2016](#)).

Additional unscheduled visits could also include repeat clinical laboratory tests in the event that a result is indicative of a clinically significant finding to assist in the determination of the resolution of an AE. Another case would be if a subject was found to have an unexplained marked reduction of visual acuity ≥ 15 letters (≥ 3 line change) of ETDRS BCVA at 4 meters (an AESI) and a repeat BCVA test was warranted sooner than the next scheduled visit.

9. ASSESSMENTS

9.1. Screening and pre-IMP dosing Assessments

Unless noted otherwise, the window period within which all screening evaluations must be completed, and the results reviewed by the investigator to confirm eligibility of participants, is from 6 weeks to one day prior to dosing with IMP. Baseline evaluations (with the exception of those tests that are only performed at the first screening visit) will be regarded as those performed immediately prior to IMP dose administration on Day 1 (Week 1 [Visit 2]).

9.1.1. Demographics

Participant demographic and baseline characteristic data to be collected on all participants include: date of birth, age, sex and race/predominant ethnicity.

9.1.2. Height and Weight

Height in centimeters (cm) and body weight (to the nearest 0.1 kg in indoor clothing, but without shoes) will be measured.

9.1.3. Medical, Surgical and Current Medical Conditions

Participants will provide a detailed medical, surgical, and medication usage during screening and again prior to IMP administration, in order to assess the eligibility of the participant for the study.

Any event or change in the participant's condition or health status prior to the initial administration of the IMP will be reported in the relevant medical history/current medical conditions section of the eCRF and not as an AE pre-dose.

9.2. Safety

9.2.1. Physical Examination

A complete physical examination will include:

- General appearance;
- Skin;
- Head, neck (including thyroid), ears, eyes, nose, mouth (including dentition), throat;
- Heart
- Circulation;
- Chest;
- Lungs;
- Abdomen;
- Back;
- Extremities;
- Lymph nodes; and

- Neurological examination.

After screening evaluations, an abbreviated, symptom-directed physical examination will be performed focused on changes since the previous examination, but will always include at least:

- General appearance;
- Skin;
- Heart / circulation;
- Chest / lungs;
- Abdomen; and
- Brief neurological examination.

Significant findings present prior to the administration of the IMP will be recorded in the relevant medical history/current medical conditions section of the participant's eCRF. Significant findings made after these time points and which meet the definition of either an AE or a disease-related event, will be recorded as such in the relevant section of the participant's eCRF.

9.2.2. Vital Signs

Vital signs including blood pressure, pulse rate, respiratory rate and sublingual body temperature after the participant has been resting for 5 minutes in a seated position as stipulated in the study schedule ([Section 1 Study Schedule of Events](#)).

The vital signs' normal ranges will be defined by site.

9.2.3. 12-lead ECG

Standard, 12-lead ECGs will be performed at Screening and nominal Weeks 4, 52, and 64. The clocks on all ECG machines will be synchronized with the central clock on a daily basis. Participants will rest for at least 5 minutes prior to the start of recording. ECG tracings will be retained and labeled as per SOPs at each clinical site.

Real-time interpretation of the tracings will be made on-site with special attention being given to changes in PR-, QRS- and QT-intervals as well as T-wave morphology changes and dysrhythmias. The QTc interval corrected for heart rate using the Fridericia formula [$QTcF = QT/RR^{(1/3)}$] ([Fridericia 1920](#)) will be calculated. Any change > 450 msec will be considered clinically significant. Any clinically significant findings will be discussed with the LMM and sponsor. The investigator will sign and date each ECG as evidence of their review.

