In the *in vitro* human ether-a-go-go related gene (hERG) channel electrophysiology assay, the 50% maximal inhibitory concentration (IC₅₀) value for inhibition of hERG tail current was 1.1 μ M (equivalent to 0.510 μ g/mL), a relatively low micromolar value and approximately equivalent to the predicted plasma concentration at the maximum proposed dose in humans. However, there were no adverse effects observed in the ECG evaluations (including QTc interval) conducted in *in vivo* oral and IV cardiovascular and pulmonary safety pharmacology studies in dogs, and in repeat dose oral toxicity studies in dogs of up to 52 weeks in duration, in which plasma tafenoquine concentrations of ~18.4 μ g/mL and greater were achieved. In addition, there were no remarkable effects on action potential parameters in an *in vitro* dog isolated Purkinje fiber assay at concentrations up to 10 μ M. Therefore, tafenoquine has a low potential for QTc prolongation, which is supported by thorough QT/QTc clinical investigations (Green 2014).

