10. Urine drug screen positive for cocaine, methamphetamine, amphetamines, methamphetamines, barbiturates, benzodiazepines, methadone, opiates, phencyclidine, or tetrahydrocannabinols. Note urine drug screen positive for tricyclic antidepressants or benzodiazepines is allowed if participant reports prescription use for a stable medical/psychiatric condition. Limited use of prescription or non-prescription medications containing codeine and not believed to affect participant safety or the overall results of the study, may be permitted on a case-by-case basis following approval by the Investigator (in consultation with the Medical Monitor, as appropriate).
11. Blood alcohol level > 0.0 determined using an alcohol breathalyzer. Note on interviewing the participant, the investigator may allow enrolment if they are satisfied the participant does not have alcohol dependence and can successfully complete the study protocol. A second blood alcohol test level > 0.0 at Week 1, Day 1 (Visit 2) would constitute grounds for exclusion of the participant.
12. Participants with medical history that might compromise their ability to comply with the protocol.
13. History of cancer (excluding basal or squamous cell carcinomas).
14. Have a clinically significant ECG as determined by the investigator or QTc interval corrected for heart rate using the Fridericia formula ($QTcF$) > 450 msec.
15. Hemoglobin, platelet counts or neutrophil counts outside the local laboratory reference range and are judged by the investigator to be clinically significant. A laboratory test may be repeated once during screening at the discretion of the Investigator. A subject with a hematology result outside the local laboratory reference range may be admitted to the study if the result is judged as not clinically significant.
16. Alanine aminotransferase (ALT), aspartate aminotransferase (AST), total or direct bilirubin, gamma glutamyl transferase (GGT) or creatinine > 1.5 times the upper limit of normal (ULN) and are judged by the investigator to be clinically significant. A laboratory test may be repeated once during screening at the discretion of the. If other biochemistry tests fall outside the local laboratory reference range, the subject may be admitted to the study if the out-of-range result is judged as not clinically significant by the investigator.

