 - Elective or pre-planned treatment for a pre-existing condition that is unrelated to the trial and has not worsened since the start of the IMP;
 - Treatment on an emergency outpatient basis for an event not fulfilling any of the definitions of an SAE given above and not resulting in hospital admission;
 - Cosmetic surgery or for social reasons or respite care in the absence of any deterioration in the participant's general condition;
- Results in persistent or significant disability/incapacity;
- Is a congenital abnormality/birth defect;
- Is considered medically important (medical and scientific judgment should be exercised in deciding whether other AE/ADRs are to be considered serious, such as important medical events that may not be immediately life threatening but may jeopardize the participant or may require intervention to prevent one of the other outcomes listed in the definition above. Examples of such events are: intensive treatment in an emergency room or at home for allergic bronchospasm; blood dyscrasias; convulsions that do not result in hospitalization; development of drug dependency or drug abuse); and
- For the purpose of this protocol an AE will be considered as serious should the AE constitute a possible Hy's Law case (defined as a participant with any value of ALT or AST greater than or equal to 3x upper limit of normal (ULN) together with an increase in bilirubin to a value greater than 2x ULN (>35% direct) and NOT associated cholestasis (ALP value less than 2x ULN).

A **non-serious** AE/ADR is any symptom or sign, which does not fulfill any of the above-mentioned seriousness criteria.

A **Safety Critical Adverse Event** is any adverse event and/or laboratory abnormality identified in the protocol as critical to safety evaluations that should be reported to the sponsor according to the reporting requirements specified in the protocol.

A **Significant Safety Issue (SSI)** is any safety issue that could adversely affect the safety of participants or materially impact on the continued ethical acceptability or conduct of the trial.

A **Suspected Unexpected Serious Adverse Reactions (SUSAR)** is any SAE where a causal relationship with the IMP is at least a reasonable possibility, but the event is not listed in the [60P IB](#).

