An **Urgent Safety Measure (USM)** is any measure required to be taken in order to eliminate an immediate hazard to a participant's health or safety. This type of significant safety issue can be instigated by either the investigator or sponsor and can be implemented before seeking approval from HREC/IRBs or Institutions.

An **Unanticipated Problem Involving Risk to Subjects or Others** (UPIRTSO) is defined as any problem or event which, in the opinion of the local investigator, was unanticipated, places participants or others at a greater risk of harm than was previously known or recognized, and was possibly related to the research procedure.

An **Adverse Events of Special Interest (AESIs)** for this study are defined as:

1. Hepatic:
 - a. Possible Hy's law case: defined as a participant with any value of ALT or AST above 3x ULN together with an increase in bilirubin to a value higher than 2x ULN and not associated with cholestasis (ALP value less than 2x ULN) (to be reported as an SAE as detailed above);
 - b. Any ALT or AST above 3x ULN;
 - c. Any elevation in bilirubin 2x ULN;
 - d. Any AST or ALT above 2x ULN and (total bilirubin [TBL] >1.5x ULN); and
 - e. Any AST or ALT above 2x ULN with the appearance of fatigue, nausea, vomiting, right upper quadrant pain or tenderness, fever, rash and/or eosinophilia (eosinophil percent or count above the ULN).
2. Ophthalmic:
 - a. Functional change on microperimetry test showing an abnormality in the paracentral region forming a ring or partial ring.
 - b. New abnormality by FM-100 hue test.
 - c. Significant deterioration in the Mars letter contrast sensitivity test with a change exceeding 0.12 logCS.
 - d. Unexplained marked reduction of visual acuity ≥ 15 letters that persists for ≥ 2 visits separated by at least one week.
 - e. A ≥ 15 letter change [≥ 3 lines] change in ETDRS BCVA at 4 meters.
3. Hematologic
 - a. Methemoglobin > 10%.
4. Other:
 - a. Any other AE that, in the opinion of the investigator, is related to the IMP and may jeopardize the participant's safety.

Although not considered an AE, pregnancy in female participants will be reported as an **event of special interest** as per [Section 10.11.6](#).

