12.2.3. Safety Data

All treatment emergent AE data will be summarized separately by treatment group and by MedDRA SOC, MedDRA preferred term (PT) and severity and relationship of each AE observed.

Vital signs and routine safety laboratory data of potential clinical concern (outside local laboratory normal limits) will be summarized descriptively by treatment and time point. Both absolute values and change from baseline will be presented.

Shift tables (from the local laboratory reference range) will be generated for each treatment group to show out of range changes in laboratory parameters during the Treatment Phase.

Vital signs will be tabulated by treatment group.

The QT interval corrected for heart rate will be calculated using the Fridericia formula (QTcF) ([Fridericia 1920](#)). ECG interval data (PR, QRS, (QTcF) will be presented as summary statistics. The numbers and percentages of subjects with QTcF > 450 msec and those with clinically significant findings will be presented in a table.

Investigational medicinal product dosing and exposure over time will be summarized by treatment group and provided in a listing for each participant.

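### Section 9.2.3 sets the QTcF significance limit as a change above 450 msec, which cannot realistically be met; it should be a QTcF value above 450 msec (with a minor Hy's law wording mismatch in Section 10.11.1)

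*Combined protocol and SAP*

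**What the plan says.** **ECG.** Section 9.2.3 plans that "12-lead ECGs will be performed at Screening and nominal Weeks 4, 52, and 64". Tracings are interpreted on site in real time, QTcF is calculated by the Fridericia formula, and then: "Any change > 450 msec will be considered clinically significant". The next sentence gives the consequence: "Any clinically significant findings will be discussed with the LMM and sponsor". The investigator signs and dates each ECG.

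The same number appears in two other places as a QTcF value. Exclusion criterion 14 (Section 6.2) applies to people who "Have a clinically significant ECG as determined by the investigator or QTc interval corrected for heart rate" (Fridericia) above 450 msec. Section 12.2.3 plans that "The numbers and percentages of subjects with QTcF > 450 msec and those with clinically significant findings will be presented in a table".

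**Liver.** Section 10.11.1 defines a possible Hy's law case twice. The SAE list requires ALT or AST at or above 3x ULN, "together with an increase in bilirubin to a value greater than 2x ULN (>35% direct"), and ALP below 2x ULN. AESI item 1a requires "any value of ALT or AST above 3x ULN together with an increase in bilirubin to a value higher than 2x ULN", with the same ALP condition but no condition on the direct fraction. Item 1a also says that such a case is to be reported as an SAE, and refers back to the SAE list for this.

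**The concern.** A threshold for clinical significance should be capable of being crossed. As written, the QTcF limit is not, so the one numerical post-dose trigger in Section 9.2.3 for discussion with the LMM and sponsor is inactive. A site that reads it literally would not flag a QTcF of 460 msec under this rule; a site that guesses the intended meaning would. ECG is named in a secondary objective and a secondary endpoint, and the study extends dosing beyond the six-month window, so a working numerical flag is reasonable to want.

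The liver point is one of consistency. One named safety term has two definitions in the same section, and one of them points to the other as if they were the same.

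**Working it through.** **Inputs.** The limit is a change above 450 msec (Section 9.2.3). Baseline QTcF, b, is at most 450 msec at entry (exclusion criterion 14). Post-dose ECGs are at Weeks 4, 52 and 64 (Section 9.2.3), and 600 participants are planned (Section 5.1). The documents give no baseline QTcF distribution, so the baselines below are assumptions, apart from the upper limit of 450.

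**QTcF.** Read literally, the rule is met when the follow-up value exceeds b + 450. Because b ≤ 450, b + 450 ≥ 2b, so QTcF must more than double.

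| Assumed baseline (msec) | Literal rule met only above | Value rule met above |
|---|---|---|
| 350 | 350 + 450 = 800 | 450 |
| 400 | 400 + 450 = 850 | 450 |
| 420 | 420 + 450 = 870 | 450 |
| 450 | 450 + 450 = 900 | 450 |

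Take a rise from 400 to 460 msec. The change is 460 − 400 = 60, which is not above 450, so Section 9.2.3 is not met. The value 460 is above 450, so the participant enters the first count in Section 12.2.3.

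The rule nominally covers up to 3 × 600 = 1,800 scheduled post-dose ECGs before dropout. That is the number of readings under the rule, not a number lost or misclassified.

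**Hy's law.** Assume bilirubin 2.4x ULN and ALP 1.0x ULN, which satisfy both texts, and vary the rest:

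| Case | ALT (x ULN) | Direct fraction | SAE list | AESI item 1a |
|---|---|---|---|---|
| a | 3.5 | 50% | yes | yes |
| b | 3.5 | 30% | no (not above 35%) | yes |
| c | 3.0 | 50% | yes | no (not above 3) |
| d | 3.0 | 30% | no | no |

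Cases b and c are discordant, so neither definition contains the other. They do not carry equal weight: case c exists only at exactly 3x ULN, while case b covers everything above 3x ULN with a direct fraction of 35% or less. The direct-fraction condition is the difference of substance.

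Reporting of the discordant cases: item 1a itself directs case b to SAE reporting, and the SAE list makes case c serious. Any discordant case has ALT or AST of at least 3x ULN and bilirubin above 2x ULN. It therefore meets AESI item 1d (above 2x ULN with total bilirubin above 1.5x ULN), and under Section 10.11.5 must be reported within 24 hours whichever definition is used.

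**The case against.** The strongest reply on the ECG is that nothing is lost in practice. The intended meaning is evident from criterion 14 and Section 12.2.3. Investigators read each tracing with attention to the PR, QRS and QT intervals, T-wave changes and rhythm, and any finding they judge significant goes to the LMM and sponsor. QTcF summary statistics and the count above 450 msec are planned regardless, and Section 2.2.1 concludes that "tafenoquine has a low potential for QTc prolongation". All of this stands, and it limits the size of the point. It does not make the written threshold correct.

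A reader might infer that ECG safety monitoring is disabled, or that the Section 12.2.3 count of clinically significant findings fails with the rule. The documents do not support either. Criterion 14 lists an investigator-determined significant ECG separately from the QTcF limit, and Section 12.2.3 tabulates the two separately, so the second count still works on investigator judgment.

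On the liver, a reader might infer that the two definitions would produce different SAE counts by arm. That is not shown. Neither entry expressly excludes the other's cases, and following both instructions sends b and c to SAE reporting. The general definition of a non-serious event could be argued against case b, so tidying is fair, but a difference arises only if a site disregards one instruction. Clinically significant laboratory results also reach the DSMB through the LMM (Section 9.2.4), and shift tables for ALT, AST and total bilirubin are planned (Section 12.2.1).

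**Conclusion.** The QTcF point holds. Section 9.2.3 states a threshold that cannot realistically be crossed, and the protocol's own use of 450 msec elsewhere supplies the correction. What is affected is the numerical trigger for discussion with the LMM and sponsor. The absolute QTcF count, the summary statistics and investigator escalation are unaffected. This rests on reading the sentence as referring to QTcF, which it directly follows, and on the entry limit of 450 msec.

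The Hy's law mismatch is real but minor. No event rate is given, so no count is estimated. The Study Safety plan and safety manual that the protocol cites are not part of the documents, and part of the SAE reporting text in Section 10.11.4 was not available; any of these may hold an operating definition.

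The point deserves correction because the ECG threshold is wrong and nearly free to put right, not because a result is at risk. The primary endpoint, sample size and power are not affected.

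**What to change.** In Section 9.2.3, replace the sentence with *Any QTcF > 450 msec will be considered clinically significant*, in line with criterion 14 and Section 12.2.3. QTcF is already calculated, so the cost is one wording change and a line in site training. There is a small downside: every QTcF above 450 msec then becomes clinically significant, so the first count in the Section 12.2.3 table becomes a subset of the second. A table footnote should say so.

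In Section 10.11.1, use one Hy's law definition, word for word, in both places, with the sponsor's reason for the choice. Total and direct bilirubin are already measured (Section 9.2.4). Keeping the SAE-list text leaves cases with 35% direct or less as 24-hour AESIs that are not automatically SAEs. Using the item 1a text means a case at exactly 3x ULN is no longer automatically an SAE. Wording that keeps what the two texts send to SAE reporting when read together would be at or above 3x ULN with no direct-fraction condition; it would also add cases such as d, which neither text now covers. The documents do not settle which is right, only that the two should agree.

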9.2.4. Laboratory Evaluations

Evaluations of standard laboratory parameters will be performed as part of the screening and baseline determinations of eligibility, as well as throughout the follow-up period as part of the safety assessments. Details of the timing of these evaluations are presented in [Section 1 Study Schedule of Events](#) and in [Section 8 Visit Schedule](#).

The investigator will document the clinical significance of all results falling outside of the normal reference ranges. All abnormal laboratory test results judged as being clinically significant by the investigator, will be reported to the LMM (and in turn the Data Safety Monitoring Board [DSMB]) and will be recorded as an AE. Repeated evaluations are

mandatory until normalization of the result(s) or until the change is no longer considered clinically significant.

Hematology

The following standard parameters will be assessed at all relevant time-points:

- RBC count, Hb, Hct, MCH, MCV, Plt count, WBC count with differential (neutrophils, lymphocytes, monocytes, eosinophils and basophils); and

A manual blood smear will be reviewed if immature/abnormal cells are detected on the automated differential or if an automated differential is not able to be performed

- MetHb %.

The methemoglobin assay is only performed at Clinipath's laboratory at the Mount Hospital (in Australia). Due to the short sample stability requirements, this sample must be routed/shipped to the Mount Hospital (or US equivalent laboratory) within 90 minutes of collection, to ensure analysis occurs within the 4-hour stability window period. An optical absorbance measurement will be taken using a Gem4000 analyzer (or equivalent). The Final Clinical Study Report (FCSR), will document the assay(s) used to measure methemoglobin.

Biochemistry

The following parameters will be measured at all relevant time-points:

- BUN, creatinine, potassium, sodium, AST, ALT, ALP, GGT, total and direct bilirubin.

Serology and other special laboratory investigations

- All participants will be screened for HBsAg, anti-HCV, anti-HIV-1 and anti-HIV-2 antibodies (if positive confirmed by a second test as per laboratory protocol).
- G6PD status will be determined at Screening.

Alcohol breath test, urine drug screen

- A urine screen for drugs of abuse (amphetamines, methamphetamines, barbiturates, benzodiazepines, cocaine, methadone, opiates, phencyclidine, tetrahydrocannabinols, and tricyclic antidepressants); and
- An alcohol breathalyzer test (Screening [Visit 1a] and Week 1, Day 1 [Visit 2] only).

Urinalysis

Urine will be collected for dipstick analysis with microscopy, as applicable, by a specified study lab.

The following parameters will be assessed: specific gravity, pH, glucose, protein, blood, ketones, leukocyte esterase, and nitrates. Microscopic examination will be performed if blood, leukocyte esterase, or nitrates are positive. Culture and sensitivity will be performed, if indicated, by the microscopy results.

Pregnancy

All WOCBP participants will have a serum β -HCG measurement at Screening and the Week 64 EOS visit. A urine β -HCG test will be undertaken prior to first IMP dose (Week 1 [Visit 2]) and at Week 4, 12, 24 and 52 visits.

Females who are menopausal will have this status confirmed by a serum FSH test at Screening.

If a participant is found to have a positive urine pregnancy test at any stage during the study, a confirmatory serum β -HCG will be performed. If confirmed positive, the participant will be discontinued from IMP and followed as described in [Section 10.11.6](#).

